### **6.3. Early Termination Visit and Follow-Up Visit**

All patients withdrawing from the study prior to Week 104 will complete an Early Termination visit. The Early Termination visit procedures are identical to those of Week 104. An endometrial biopsy is required for all patients at the Early Termination visit except for patients whose last dose of study drug was taken during Week 32 or earlier or within four weeks after completion of the Week 52 endometrial biopsy. However, the endometrial biopsy may be obtained if it will aid in the evaluation of an ongoing adverse event. Follow-up bone densitometry findings for patients who terminate from the study early will proceed according to the rules provided in Section 6.5.2.6.

Patients (including those who complete the Week 104 visit and those who withdraw early from this study) will have a Follow-Up visit approximately 30 days after the last dose of study drug, or prior to the date of initiation of another investigational agent or hormonal therapy affecting the hypothalamic-pituitary-gonadal axis or surgical intervention or other invasive procedure for endometriosis, whichever occurs first. However, for patients who enroll directly into another relugolix clinical study upon completion of the Week 104 visit, the Follow-Up visit may be waived.

The Follow-Up visit will be used to assess safety after discontinuation of study treatment including adverse events, clinical safety laboratories, and return of menstruation. Refer to the Schedule of Activities (see Section 1.1) for individual study visit procedures during the Follow-Up visit.

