	
Secondary Efficacy Endpoints
 
To be assessed at Week 52 and Week 104, unless otherwise specified
 
 
• Change from the parent study Baseline in the EHP-30 Pain Domain scores;
 
• Change from the parent study Baseline in the mean dysmenorrhea NRS score;
 
• Proportion of patients who are better or much better on the PGIC for dysmenorrhea (at Week 52 only);
 

	
 
• Change from the parent study Baseline in the mean NMPP NRS score;
 
• Change from the parent Baseline in the mean NRS score;
 
• Proportion of patients not using opioids;
 
• Proportion of patients not using analgesics;
 
• Proportion of patients who are better or much better on the PGIC for NMPP (at Week 52 only);
 
• Change from the parent study Baseline in the mean dyspareunia NRS scores;
 
• Proportion of patients who are better or much better on the PGIC for dyspareunia (at Week 52 only);
 
• Change from the parent study Baseline in the mean dyspareunia functional impairment on the sB&B scale;
 
• Change from the parent study Baseline in severity scores on the PGA for pain;
 
• Proportion of responders based on their EHP-30 Pain Domain score;
 
• Change from the parent study Baseline in function impairment on the PGA for function;
 
• Change from the parent study Baseline in each of the non-pain EHP-30 domains (Control and Powerlessness, Social Support, Emotional Well-Being, and Self-Image);
 
• Change from the parent study Baseline pain assessment period in dysmenorrhea-related functional effects (sB&B);
 
• Change from the parent study Baseline pain assessment period in NMPP-related functional effects (sB&B).
 

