Dispense or Prescribe Protocol-Specified Analgesic Drugs u	X	X	X	X	X	X	X	X	X		X h	
Treatment Compliance		X	X	X	X	X	X	X	X	X	X h	
Take Study Drug Dose in Clinic	X v					X				X	X h	
Daily Self-Administration of Study Treatment w		X ----- X										
Take Protocol-Specified Rescue Analgesics as Needed x		X ----- X										
EHP-30 Questionnaire y	X g		X		X	X		X		X	X h	

VISIT NAME (Timing is relative to MVT-601-3101/-3102)	PERIOD											SAFETY FOLLOW-UP
	Week 24/Baseline (Week 24 of Parent Study; Baseline of Extension Study)	Week 28 and Week 32	Week 36	Week 40 and Week4 4	Week 48	Week 52 a	Week 65	Week 78	Week 91	Week 104 a / Early Termination	Un- scheduled b	Follow-Up c (~30 days after last dose of study drug)
Visit Window (days)	Parent Study Day 169 -10/+20	±7	±7	±7	±7	±7	±7	±7	±7	±7	-	-3 to +18
Patient Global Assessment for Pain y	X g	X	X	X	X	X	X	X	X	X	X h	
[on paper] Patient Global Assessment for Function z	X g	X	X	X	X	X	X	X	X	X	X h	
Patient Global Impression of Change y	X g		X			X					X h	
[on paper] EHP Work Domain z	X g					X		X		X	X h	
EQ-5D-5L Questionnaire y	X g					X		X		X	X h	
Adverse Event Collection aa	X	X	X	X	X	X	X	X	X	X	X	X
Status of Menstruation Recovery												X bb,cc
Telephone Contact cc						X (W57)	X (W71)	X (W85)	X (W98)			
Mammogram dd						X dd				X dd	X dd	

BP = blood pressure; DXA = dual-energy x-ray absorptiometry; ECG = electrocardiogram; eDiary = electronic diary; EHP = Endometriosis Health Profile; EQ-5D-5L = European Quality of Life Five-Dimension Five-Level Scale; HR = heart rate; NRS = Numerical Rating Scale; PGA = Patient Global Assessment; sB&B = Subject Modified Biberoglu and Behrman; W = week.

a The Week 52 visit should occur on or after the 1-year anniversary of Baseline Day 1 of the parent study ( $\pm 7$  days), and the Week 104 visit should occur on or after the 2-year anniversary of Baseline Day 1 of the parent study.

b Unscheduled visits may be conducted at the investigator's discretion when needed. The reason for the visit will be captured in the source documents.

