#### **6.5.1.5. Patient Global Assessment and Patient Global Impression of Change**

These simple questions are used by the patient to qualitatively describe severity of pain or effects on function (PGA) or impression of change in pain severity (PGIC) (see [Appendix 5](#)) on a schedule described in the Schedule of Activities (Section 1.1). Patients should answer these questions before other types of study procedures, such as blood draws and physical examinations, are performed. The PGA for pain severity and the PGIC will be completed on a tablet device at the study site. The PGA for function will be completed on a paper questionnaire at the study site.

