For any pain assessment period (Baseline or visit-specific), the average NRS scores will be calculated for dysmenorrhea and NMPP separately. An average NRS score for dysmenorrhea is calculated as the average NRS score over the days with menses during a given pain assessment period. An average NRS score for NMPP is calculated as the average NRS score over the days without menses during a given pain assessment period. The analgesic use for a given pain assessment period is summarized by total dose count defined as the average daily dose count taken during the given pain assessment period multiplied by 35. Additional details on calculating dose counts and on the precise definition of an increase in analgesic use will be provided in the SAP.

Descriptive statistics will be provided for efficacy endpoints (listed below) similar to those used for the parent studies at Week 52 and Week 104.

- Change from the parent study Baseline in the EHP-30 Pain Domain scores;
- Change from the parent study Baseline to in the mean dysmenorrhea NRS score;
- Proportion of patients who are better or much better on the PGIC for dysmenorrhea;
- Change from the parent study Baseline in the mean NMPP NRS score;
- Change from the parent Baseline in the mean NRS score;
- Proportion of patients not using opioids;
- Proportion of patients not using analgesics;
- Proportion of patients who are better or much better on the PGIC for NMPP;

- 
- Change from the parent study Baseline in the mean dyspareunia NRS scores;
  - Proportion of patients who are better or much better on the PGIC for dyspareunia;
  - Change from the parent study Baseline in the mean dyspareunia functional impairment on the sB&B scale;
  - Change from the parent study Baseline in severity scores on the PGA for pain;
  - Proportion of responders based on EHP-30 Pain Domain scores;
  - Change from the parent study Baseline in function impairment on the PGA for function;
  - Change from the parent study Baseline in each of the non-pain EHP-30 domains (Control and Powerlessness, Social Support, Emotional Well-Being, and Self-Image);
  - Change from the parent study Baseline pain assessment period in dysmenorrhea-related functional effects (sB&B);
  - Change from the parent study Baseline pain assessment period in NMPP-related functional effects (sB&B).

For binary endpoints, the point estimate and 2-sided 95% CI for the proportion will be provided by parent study treatment group.

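### PGIC is not scheduled at Early Termination, so women who stop before Week 52 give no rating when they stop; separately, Section 9.4 lists PGIC for Week 104 against the Week 52 limit set elsewhere

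*Protocol*

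**What the plan says.** **Collection.** The row "Patient Global Impression of Change" in Table 1-1 (Section 1.1) is marked at Week 24/Baseline, Week 36 and Week 52, and optionally at Unscheduled visits. The cells for Weeks 65, 78 and 91 and for Week 104/Early Termination are empty. Section 6.5.1.5 has PGIC completed "on a schedule described in the Schedule of Activities (Section 1.1"), so the table governs. Section 6.3 adds: "The Early Termination visit procedures are identical to those of Week 104".

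**Endpoint timing.** The Synopsis lists "Proportion of patients who are better or much better on the PGIC for dysmenorrhea (at Week 52 only") and "Proportion of patients who are better or much better on the PGIC for NMPP (at Week 52 only"), and limits dyspareunia in the same way. Section 3 repeats the limit for all three. Section 9.4 has this instead: "Descriptive statistics will be provided for efficacy endpoints (listed below) similar to those used for the parent studies at Week 52 and Week 104". The list under that sentence includes all three PGIC items with no time limit, for example "Proportion of patients who are better or much better on the PGIC for dyspareunia".

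**Contrast and analysis rules.** The Synopsis and Section 3 define the first pair of primary endpoints at Week 52/Early Termination, from NRS scores. Section 9.2 makes the efficacy population everyone enrolled and dosed in the extension. Section 9.4 leaves missing-data handling to the SAP.

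**The concern.** A woman who leaves between Week 24 and Week 52 attends an Early Termination visit and completes the tablet questionnaires, but she is not asked the three PGIC questions. Her view of her treatment at the moment she gives it up is not recorded for three secondary endpoints (dysmenorrhea, NMPP and dyspareunia). PGIC is the patient's own overall judgement and cannot be rebuilt from daily diary scores. Whatever rule the SAP adopts, it must work with an older rating or none.

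If women who stop differ from those who stay, the Week 52 proportions may misdescribe the extension population. They would also rest on a different information base from the primary endpoints, which make provision for a value at termination.

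The Section 9.4 wording is a separate matter. Read literally, it commits the Week 104 report to PGIC summaries for which no data are scheduled.

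**Working it through.** The protocol states no figure to reproduce here. The check is a reading of the schedule against the endpoint text, followed by a short calculation showing what the gap leaves undetermined.

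**1. Is the empty cell real?** Other questionnaire rows in the same 12-column table serve as alignment controls.

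| Row | Marked at |
|---|---|
| PGIC | W24, W36, W52, Unscheduled |
| PGA for pain | every column from W24 to W104/Early Termination, Unscheduled |
| EHP-30 | W24, W36, W48, W52, W78, W104/Early Termination, Unscheduled |
| EHP Work Domain | W24, W52, W78, W104/Early Termination, Unscheduled |

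All three control rows carry a mark at Week 104/Early Termination, as do PGA for function and EQ-5D-5L. Only PGIC does not, so the gap is not an effect of the text extraction. The Unscheduled mark carries footnote h, which makes the procedure optional and dependent on the purpose of the visit. It does not create a rating at termination.

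**2. Last scheduled rating for a woman who stops before Week 52.**

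- Stops before the Week 36 visit: Week 24, taken as a parent-study procedure (footnote g).
- Stops after the Week 36 visit: Week 36, which can be close to 52 − 36 = 16 weeks old.
- Former placebo patients (Group C) who stop before Week 36: the Week 24 rating was given before the first extension dose, so they have no scheduled PGIC on relugolix.

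**3. Timing statements side by side.**

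| Place | PGIC timing |
|---|---|
| Table 1-1 | last scheduled at Week 52 |
| Synopsis, endpoints | Week 52 only |
| Section 3, endpoints | Week 52 only |
| Section 9.4 | Week 52 and Week 104 |

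Three places agree and one does not. The objectives heading also names both weeks, but it is a general heading, and in Section 3 the paired endpoint column supplies the limit.

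**4. What the missing ratings leave open.** Let *d* be the fraction of the population without a Week 52 PGIC, *p* the proportion better or much better among those rated, and *q* the unknown proportion among the rest.

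- All patients: (1 − *d*)*p* + *dq*
- Observed minus all patients: *d*(*p* − *q*). This is positive, zero or negative according to whether *q* is below, equal to or above *p*.
- Limits with *q* = 0 and *q* = 1: (1 − *d*)*p* to (1 − *d*)*p* + *d*, a width of exactly *d*.

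The protocol gives none of *d*, *p* or *q*. The values below are assumptions, chosen only to show the range. Counts use the planned enrolment of about 800.

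| *p* | *d* | Rated at Week 52 | Lower limit | Upper limit |
|---|---|---|---|---|
| 0.80 | 0.05 | 800 × 0.95 = 760 | 0.95 × 0.80 = 0.76 | 0.76 + 0.05 = 0.81 |
| 0.80 | 0.30 | 800 × 0.70 = 560 | 0.70 × 0.80 = 0.56 | 0.56 + 0.30 = 0.86 |
| 0.60 | 0.30 | 560 | 0.70 × 0.60 = 0.42 | 0.42 + 0.30 = 0.72 |

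These limits show how much is unknown. They do not estimate bias.

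**The case against.** The best defence has four parts.

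- **Week 52 only looks deliberate.** The schedule and both endpoint lists agree on it, so Section 9.4 has simply failed to repeat the limit. This stands. A reader might infer that a planned Week 104 PGIC endpoint has been lost for want of data; the documents do not support that, because neither endpoint list defines one.
- **Missing data belong to the SAP.** A reader might infer that the Week 52 PGIC analysis is restricted to completers. The protocol does not say so. The population is everyone enrolled and dosed, Week 24 and Week 36 ratings exist, and the SAP may count missing ratings as not improved or use another rule. Completion is also defined by the Week 104 visit, not Week 52. This stands against any claim about the analysis rule. It does not answer the collection point, because no rule can recover an answer that was never requested.
- **Other patient-reported measures are taken at termination.** PGA, EHP-30 and EQ-5D-5L are scheduled there, and the primary endpoints come from the diary, which is a different route. This limits the damage, but none of these measures supplies the PGIC response that the three endpoints need.
- **The endpoints are secondary and descriptive.** Section 9 plans no formal treatment comparisons. This lowers the stakes without removing the gap.

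Recall back to the start of treatment is a fair argument against asking PGIC at Week 104. It has less force for women who leave before Week 52, since PGIC is asked at Week 52 itself.

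**Conclusion.** Two points hold. First, women who terminate before Week 52 have no scheduled PGIC at termination, unlike the primary endpoints, which are defined at Week 52/Early Termination. The three Week 52 PGIC proportions may be biased as a result if early stoppers differ from those who stay. Second, Section 9.4 contradicts the Synopsis, Section 3 and the schedule on Week 104 PGIC; this is a wording error.

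No size or direction can be attached to the first point. Upward bias is a natural inference, but it requires that dropouts respond less often than those rated and that the SAP does not already allow for this. The documents establish neither. What can be said without assumptions about response is that the undetermined range is as wide as the fraction without a Week 52 rating. The point is worth correcting because the remedy is cheap and an untaken rating cannot be obtained later.

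**What to change.** 1. Add the three PGIC items to the tablet battery at Early Termination visits that occur before Week 52. In Table 1-1 this is one mark in the Week 104/Early Termination column, with a footnote restricting it to those visits, and a matching exception in Section 6.3. The cost is three extra questions at a visit where the tablet is already in use.
2. In Section 9.4, attach the Week 52 limit to each of the three PGIC items so that they agree with the Synopsis and Section 3. The cost is wording only.

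How a termination rating, or a missing one, enters the Week 52 proportion should be left to the SAP. The new collection helps only women who have not yet stopped or reached Week 52 when it takes effect. Section 6.5.2.6 already provides for women who left or finished before Amendment 3.1, so some will be past the point where it can help.

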## 6.4. Unscheduled Visits

Unscheduled visits may be performed at any time during the study whenever necessary to assess for or follow-up on adverse events, at the patient's request, or as deemed necessary by the investigator. The date and reason for the Unscheduled visit should be recorded in the source documentation. The following activities should be completed at Unscheduled visits: recording of reason for the visit, concomitant medication review, and evaluation of adverse events. In addition, procedures such as vital signs, weight, complete physical examination, sign- and symptom-directed physical examination, clinical laboratory assessment, urinalysis, urine pregnancy testing, pharmacodynamic sampling, mammogram (for patients required to have this procedure; see Section 6.5.2.9), 12-lead ECG, study drug compliance and dispensation, eDiary review, dispensation or prescription of protocol-specified analgesics, etc., may be conducted as needed. See the Schedule of Activities (Section 1.1) for tests that may be performed, as indicated at an Unscheduled visit. The investigator should consult with the medical monitor, if needed, to discuss Unscheduled visit testing. The investigator should obtain approval from the sponsor to perform an unscheduled endometrial biopsy or DXA, unless urgently indicated.

## 6.5. Study Procedures

### 6.5.1. Efficacy-Related Procedures

#### 6.5.1.1. Pharmacodynamics Sample Collection

A blood sample for the pharmacodynamic analysis of serum estradiol will be collected predose at the visits indicated in the study Schedule of Activities (see Section 1.1), other than at the Week 104 or the Early Termination visit, when no dose is administered. These pharmacodynamic samples will be analyzed at a central laboratory. These results will not be shared with the sites at any time.

#### 6.5.1.2. Patient eDiary

All women enrolled in the study will continue to use the patient eDiary dispensed in the parent study (see Appendix 2). Patients will complete daily eDiary entries, including NRS pain scores, menstruation information, analgesic drug use, date and time of study drug administration, and sB&B scale scores until Week 52. After Week 52, eDiary scores will be entered over four eDiary collection cycles on the following schedule: Week 57 to the Week 65 visit, Week 71 to the Week 78 visit, Week 85 to the Week 91 visit, and Week 98 to the Week 104 visit.

The site should review the eDiary data at every visit.

#### 6.5.1.3. Endometriosis Health Profile-30

The EHP-30 is used to evaluate the functional impact and the quality of life of patients with endometriosis (see Appendix 3). Patients will complete the EHP-30 questionnaire at the site at visits indicated in Section 1.1 before other types of study procedures, such as blood draws and physical examinations, are performed. The EHP-30 will be completed on a tablet device at the study site.

#### **6.5.1.4. European Quality of Life Five-Dimension Five-Level Scale**

The EQ-5D-5L is a standardized instrument for use as a measure of health outcomes (see [Appendix 4](#)). Mobility, self-care, usual activities, pain/discomfort, and anxiety/depression are each assessed on a 5-level categorical scale.

Patients will complete the EQ-5D-5L questionnaire at the site at visits indicated in Section 1.1 before other types of study procedures, such as blood draws and physical examinations, are performed. The EQ-5D-5L will be completed on a tablet device at the study site.

#### **6.5.1.5. Patient Global Assessment and Patient Global Impression of Change**

These simple questions are used by the patient to qualitatively describe severity of pain or effects on function (PGA) or impression of change in pain severity (PGIC) (see [Appendix 5](#)) on a schedule described in the Schedule of Activities (Section 1.1). Patients should answer these questions before other types of study procedures, such as blood draws and physical examinations, are performed. The PGA for pain severity and the PGIC will be completed on a tablet device at the study site. The PGA for function will be completed on a paper questionnaire at the study site.

#### **6.5.1.6. Endometriosis Health Profile Work Domain**

This 5-question paper questionnaire will be completed by the patient to describe the effects of endometriosis on their work ([Appendix 6](#)). Patients will complete the EHP Work Domain questionnaire at visits indicated in Section 1.1 before other types of study procedures, such as blood draws and physical examinations, are performed. The EHP Work Domain will be completed on a paper questionnaire at the study site.

### **6.5.2. Safety-Related Procedures**

#### **6.5.2.1. Weight**

Patients should have weight and height measured while wearing indoor clothing and with shoes removed.

#### **6.5.2.2. Vital Signs**

Vital signs, including blood pressure, heart rate, and temperature, should be measured in the seated position after 5 minutes of rest.

#### **6.5.2.3. Physical Examinations**

A complete physical examination will include head, ears, eyes, nose, mouth, thyroid, skin, heart and lung examinations, lymph nodes, gastrointestinal, skeletal, and neurological systems. All subsequent physical examinations should focus on signs and symptoms reported by the patient to assess for clinically significant changes from the Baseline assessment. The physical examinations at Week 52 and Week 104 will include a breast examination.

#### 6.5.2.4. Clinical Laboratory Samples

All protocol-required laboratory assessments must be conducted in accordance with the Investigator Site File and the protocol Schedule of Activities (see Section 1.1). Laboratory requisition forms must be completed and samples must be clearly labelled with the Patient ID number, protocol number, site/center number, and visit date. Details for the preparation and shipment of samples will be provided. Reference ranges for all safety parameters will be provided to the site by the central laboratory.

The samples collected for clinical laboratory tests are listed in [Table 6-1](#).

**Table 6-1 Clinical Laboratory Tests**

Chemistry	Hematology	Urinalysis
Potassium	White blood cell count	Protein
Chloride	White blood cell differential	Glucose
Bicarbonate	Red blood cell count	Blood
Blood urea nitrogen	Hemoglobin	Urobilinogen
Creatinine	Hematocrit	Bilirubin
Glucose	Mean corpuscular volume	Color and clarity
Calcium	Platelet count	pH
Phosphate	Red blood cell morphology	Leucocyte esterase
Magnesium		Ketones
Sodium		Nitrite
Albumin		Specific gravity
Creatine kinase		Urine microscopy (reflex testing based on abnormal urine analysis)
Hemoglobin A1c		
Bilirubin total		
Alanine aminotransferase		
Aspartate aminotransferase		
Gamma-glutamyl transferase		
Alkaline phosphatase		
Hormones	Lipids	Pregnancy
Estradiol	Total cholesterol	Pregnancy test (human chorionic gonadotropin)
	Low-density lipoprotein	
	High-density lipoprotein	
	Triglycerides	

The central laboratory will perform laboratory tests for chemistry, hematology, urinalysis, and serum hormone levels. Each study site will conduct urine pregnancy tests locally.

All laboratory tests with values that are considered abnormal and clinically significant during participation in the study or within 30 days after the last dose of study drug should be repeated until the values return to normal, baseline, or have stabilized. Abnormal values, determined to be clinically significant, should be reported as adverse events.

For patients with incomplete recovery of bone mineral density loss at the 6- and 12-month post-treatment follow-up visit, clinical laboratory tests should be performed (see Section 6.5.2.6). These laboratory assessments will be submitted to the central laboratory. If these laboratory assessments are scheduled to occur after the study database is locked, they will be performed at a local laboratory. The investigator will maintain a copy of the reference ranges (with the record of the reference ranges) for the laboratory or laboratories used.

